9.3 Populations for Analyses

Population for Analysis: All enrolled subjects who underwent the HepQuant SHUNT Test; a maximum of N=420 and minimum of N=400 will be analyzed (the interim analysis will be conducted when DSI and EGD exam results are available in the analysis dataset for approximately N=250 participants).

Safety Analysis Dataset: All enrolled subjects who underwent the HepQuant SHUNT Test; a maximum of N=420 and minimum of N=250 will be analyzed.

- Per-Protocol Analysis: All enrolled subjects who completed the entire protocol
- Other Datasets that may be used for sensitivity analyses: None

9.4 Statistical Analyses

9.4.1 GENERAL APPROACH & DESCRIPTIVE STATISTICS

Selected characteristics will be analyzed for the total enrolled CLD population, and in subgroups by categories of etiology of liver disease (viral, NASH, EtOH, and cholestatic disease), and disease severity (noncirrhotic fibrosis, compensated cirrhosis (CP-A), decompensated cirrhosis (CP-B)). For descriptive statistics, categorical and continuous data will be presented as percentages, means with standard deviations, median, and range. Statistical significance will be defined by two-sided p-values <0.05 and 95% confidence intervals will be used to summarize uncertainty in estimated measures of diagnostic accuracy or differences between groups.

Appropriate covariates are pre-specified in the sections below.

[figure not shown]
9.4.2 ANALYSIS OF THE PRIMARY EFFICACY ENDPOINT(S)

[figure not shown]
Primary efficacy endpoint (DSI \leq18.3 "Rules Out" Large Esophageal Varices): The independent variable is DSI and the dependent variable is the presence/absence of large esophageal varices diagnosed by EGD within 42 days of the HepQuant SHUNT test. The sample size evaluation of section 9.2.1 is based on the large-sample variance of **Table 9** equation E. This equation cannot be used for data analysis if sensitivity is close to 1.0 (Marril, et al [118]). The following methods will be used to evaluate whether the trial results satisfy the performance goals for NLR and sensitivity:

Rule out NLR > 0.52: This objective will be satisfied if the upper limit of the confidence interval for NLR is smaller than 0.52. The score-based confidence interval that is derived by inverting the score test (see Marril, et al. [118]) will be used to calculate the NLR confidence interval. The confidence level will be chosen to assure an overall one-sided type-I error rate of 0.025 as described in section 9.5.1.

Sensitivity >= 0.85: This objective will be satisfied if the observed sensitivity is larger than 0.85. The corresponding 95% confidence interval will also be reported and will be calculated using the exact binomial distribution.

Evaluation of standard for the rule-out hypothesis (DSI ≤18.3 "Rules Out" large esophageal varices): The two performance goals can be evaluated graphically and compared with previously published studies of the diagnostic accuracy of existing tests for ruling out the presence of large varices. NLR is a function of sensitivity and specificity and can be plotted on a graph of sensitivity versus one minus specificity in a manner similar to the ROC curve. Figure 10 shows the approximate critical value for ruling out NLR > 0.52 plotted in the ROC plane, along with the critical value for sensitivity of 0.85. The shaded region of the plot represents acceptable performance. The plot includes results from the 10 previously published studies of LSM plus platelets. The plot demonstrates that the HALT-C study using DSI and half of the studies using LSM plus platelets would satisfy the standards for improved NLR in the proposed trial. We conclude that the null hypothesis (NLR >0.52) is empirically consistent with the diagnostic tests that are currently used in clinical practice, and therefore the proposed standard (ruling out NLR >0.52) is a clinically meaningful basis for the design of the SHUNT-V trial to evaluate whether DSI meets a valid standard for clinical diagnosis of large esophageal varices in the CLD population.

Abbreviations: NLR, negative likelihood ratio; cv, critical value; Se, sensitivity; Sp, specificity. DSI 18.3 is validated for "Rule Out" large esophageal varices if trial results fall in the shaded region above the blue line. The approximate critical value (NLR = 0.27) is calculated using **Table 9** equation E. The published results using LSM and platelet count are shown by their individual colored markers with the first author of the respective publication listed. The red marker with black border represents the results of DSI 18.3 from the HALT-C training dataset with sensitivity 95% and specificity 54%. The high sensitivity and higher specificity of DSI 18.3 from the HALT-C Trial demonstrated favorable diagnostic performance compared to the studies of LSM plus platelet count.

The HALT-C Training dataset (red marker with black border) showed that DSI 18.3 had sensitivity 0.95 and specificity 0.54 yielding a NLR of 0.0926, well within the shaded blue region. The upper limit of the 95% CI for NLR was 0.143, well below the upper limit of the 95% CI for the cv of 0.52. We anticipate that diagnostic performance of DSI 18.3 in the CLD Validation dataset will equal or exceed its performance in the HALT-C Training dataset, with sensitivity >95%. If that is the case, then specificity may drop below 0.50 as long as the observed NLR is <0.27. The mean value for specificity from the 10 published studies of LSM plus platelet count was 0.28 with a minimum of 0.13 and maximum of 0.44. Specificity \geq 0.28 will be considered acceptable, as long as the confidence interval rules out NLR > 0.52.

The following table shows specific values of sensitivity and specificity with 95% confidence intervals that are on the critical value line in **Figure 10**. The table shows the ranges of sensitivity and specificity that would be ruled out if the trial results are on the critical value line.

Spec	Specificity (95% CI)		ivity (95% CI)
0.25	(0.203, 0.297)	0.932	(0.878, 0.987)
0.30	(0.250, 0.350)	0.919	(0.859, 0.979)
0.35	(0.298, 0.402)	0.906	(0.841, 0.970)
0.40	(0.346, 0.454)	0.892	(0.824, 0.960)
0.45	(0.395, 0.505)	0.878	(0.807, 0.950)
0.50	(0.445, 0.555)	0.865	(0.790, 0.940)
0.55	(0.495, 0.605)	0.851	(0.774, 0.929)

Table 11: Values of sensitivity and specificity that are on the critical value line.

Evaluation of trial power: The initial power evaluation for selection of the total sample size (**Table 10**) uses the large sample variance approximation of **Table 9** equation E. A simulation study was designed and conducted to provide a full evaluation of trial power including the planned interim analysis. Power is a function of sensitivity, specificity as determined by NLR (specificity = (1-sensitivity)/NLR), and the prevalence of large varices. The simulation study calculated power as the proportion of 10000 simulated trials that satisfy the two performance goals (upper CI limit for NLR < 0.52 and sensitivity > 0.85). Key results of the simulation study are summarized in **Table 12**.

	Wi	thout Interim Analy	/sis	With Interim Analysis		sis
			20% prevalence o	f large varices		
NLR	Sensitivity = 0.85	Sensitivity = 0.90	Sensitivity = 0.95	Sensitivity = 0.85	Sensitivity = 0.90	Sensitivity = 0.9
0.52	0.020	0.017	0.011	0.020	0.015	0.007
0.40	0.146	0.088	0.041	0.131	0.077	0.032
0.30	0.502	0.380	0.157	0.417	0.348	0.124
0.20	0.524	0.916	0.583	0.520	0.855	0.545
0.15	NA	0.930	0.910	NA	0.880	0.890
			25% prevalence o	f large varices		
0.52	0.021	0.021	0.012	0.019	0.017	0.010
0.40	0.170	0.107	0.054	0.151	0.100	0.041
0.30	0.515	0.462	0.193	0.450	0.422	0.172
0.20	0.515	0.944	0.696	0.523	0.888	0.668
0.15	NA	0.945	0.956	NA	0.902	0.951
	NA denotes combi	nations that produc	ce specificity = 1.0 a	and results that ca	nnot occur in a trial	

Table 12: Power for the SHUNT-V trial with and without interim analyses. The type I error rate is the power when NLR = 0.52 and is always smaller than the target one-sided 0.025 alpha level.

9.4.3 STATISTICAL TESTS AND STEPS

The initial **statistical tests and steps** in the analysis of the **CLD Validation dataset** are:

Uni-variable Logistic Regression. The relationship of DSI (independent variable) to large esophageal varices (dependent variable) will first be evaluated by univariate logistic regression.

Multi-variable Logistic Regression. Independence of DSI as a predictor of large esophageal varices will be evaluated in multi-variable logistic regression analyses including other risk factors for varices. The current clinical gold standard for likelihood of varices and recommendation for EGD is a diagnosis of cirrhosis - by either liver biopsy or other criteria. Likelihood of large varices is further increased by increase in CP class. In BAVENO VI, platelet count was a major modifier of risk. For these reasons, we will evaluate the independence of DSI as a predictor of large esophageal varices adjusting for demographic variables, diagnosis of cirrhosis, stage of cirrhosis, and platelet count.

Area Under the Receiver Operator Curve (AUROC). The diagnostic performance of DSI for predicting large esophageal varices will be evaluated by Area under the Receiver Operating Curve (AUROC). The c-statistic for DSI in likelihood of large esophageal varices will be defined. The performance characteristics (sensitivity, specificity, PPV, NPV, NLR, PLR, FNR, miss rate⁷ and their 95% Cls) will be defined for DSI cutoff 18.3.

⁷ In this protocol, FNR is defined as 1-NPV and miss rate is defined as 1-Sensitivity. See the footnote in Section 1.1 for a discussion of these two measures.

Secondary efficacy endpoint (probability and calibration curves). We will evaluate the relationship of predicted probability of large varices versus DSI using logistic regression analysis and affiliated statistical tests of the significance of the association between the continuous DSI score and risk of large varices. These analytical results will be further evaluated using a calibration table to compare the observed probabilities of large varices in quartiles, deciles, or other categories of DSI to the expected probabilities from the logistic regression equation.

9.5 Summary and Implications of Validating the Primary Endpoint

We anticipate test performance to be similar between the HALT-C Training dataset and the CLD Validation datasets. In the HALT-C Training dataset with prevalence of large varices of 10%, DSI \leq 18.3 yielded sensitivity 95%, specificity 54%, NLR 0.0926, NPV 99%, and FNR 1%. Therefore, we expect the NLR and upper limit of the 95% CI for NLR to meet the validation criteria: upper limit of 95% CI <NLR₀, or <0.52, and observed sensitivity > 0.85. There are several clinical implications of this validation.

DSI ≤18.3 improves the diagnostic performance to "Rule Out" Large Varices. The high sensitivity and moderate specificity of DSI ≤18.3, compared to the lower sensitivity and specificity of publication of LSM plus platelet count, suggest that the DSI cutoff might perform well in identifying the cases free of large varices who might avoid screening EGD. The HALT-C Training dataset results suggested that up to 50% of screening EGDs might be avoided. In contrast, the data with LSM plus platelet count suggested that only 20% of screening EGDs might be avoided.

DSI \leq **18.3 lowers the FNR for Large Varices.** The pre-test odds of large esophageal varices is given by $[\pi/(1-\pi)]$, where π is prevalence of large varices. For prevalence of 10%, the pre-test odds (0.1/0.9) for large esophageal varices is 0.11. The post-test odds of large esophageal varices is given by: NLR x $[\pi/(1-\pi)]$. For NLR of 0.0926, the post-test odds of large esophageal varices for DSI \leq 18.3 was: 0.0926 x (0.1/0.9) = 0.0102, or a pre- to post-test reduction in odds for large varices of 11.0 – a highly significant reduction based on DSI.

In contrast, for an average NLR of 0.27 and prevalence of 11% (pre-test odds (0.11/0.89) = 0.12) from the 10 published studies of LSM plus platelet count, the post-test odds of large esophageal varices was 0.27 x (0.11/0.89) = 0.033, or odds ratio of 3.6. This comparison suggests that DSI has better diagnostic performance.

Applying these results for DSI to the CLD Validation dataset where the prevalence of large esophageal varices is projected to be 20% yields a post-test odds for large varices of $0.09 \times (0.2/0.8) = 0.0225$. In comparison, LSM plus platelets would yield a post-test odds for large varices of $0.27 \times (0.2/0.8) = 0.0675$. The data suggests that DSI has a lower FNR than LSM plus platelet count over the prevalence range of 10 to 20% for large varices.

DSI ≤18.3 lowers the Miss Rate for Large Varices. Miss rate for large varices is defined by the number of cases with large varices below cutoff divided by the total number of cases with large varices. For the HALT-C Training dataset the Miss Rate was 1/22 = 4.5%. For the pooled results from the 10 published studies of LSM plus platelet count the Miss Rate was 21/319 = 6.6%. For individual published studies of LSM plus platelet count, the Miss Rate ranged from 0.0 to 18.2%.

In addition, the AUROC for DSI in likelihood of large varices was c-statistic = 0.82 which compares favorably to cstatistic = 0.76 for LSM plus platelet count, i.e., an improvement in overall diagnostic performance.

9.5.1 PLANNED INTERIM ANALYSIS

One interim analysis is planned after the analysis data sets contain complete results (DSI measurements and EGD examination results) on at least 250 participants. The objective of the interim analysis will be to evaluate whether the interim results would allow the trial to be stopped for either efficacy or futility; i.e., because the performance goals for DSI < 18.3 as a test for ruling out large varices has been satisfied (efficacy) or because it is futile to continue because sensitivity is too low and NLR is too large.

Process for preparing and reviewing interim analysis: The trial database is maintained by an independent CRO. Trial investigators do not have access to DSI results, and the Sponsor does not have access to EGD findings. The interim analysis will therefore be performed by a statistician independent from both the sponsor and the CRO. The results of the interim analysis will be reviewed and interpreted by the independent biostatistician using the interim decision criteria to make a recommendation to HepQuant to either continue or stop the trial based on the interim results. If the determination is made to continue the trial, no further analyses will be conducted until the full recruitment is reached, and no blinded information will be provided to the sponsor, the CRO, or any investigator. If the determination is made to stop the trial, analysis of all endpoints will be performed on the interim data (N=250) according to the trial SAP.

Decision criteria for the interim analysis: The interim decision criteria are based on standard methods for group sequential clinical trial design as published by Emerson, et. al. [117] as implemented in the software package RCTdesign. With complete results on 250 subjects the independent unblinded statistician will convey one of three conclusions based on the results of the data analysis:

- i. The efficacy decision criteria have been satisfied: This conclusion is reached if:
 - a. The upper limit of the 97.64% score-based confidence interval for NLR is less than 0.52, and
 - b. the observed sensitivity greater than or equal to 0.85.
- ii. *The futility decision criteria have been satisfied:* This conclusion is reached if:
 - a. The upper limit of the 51.41% score-based confidence interval for NLR is larger than 0.52, and
 - b. the observed sensitivity less than 0.85.
- iii. Neither the efficacy nor the futility decision criteria have been satisfied.

In the case of the second conclusion, i.e., futility, the trial will be stopped; the assessment of futility represents a binding assessment.

In the case of the third conclusion, the trial will continue to the full sample of 400 subjects with complete data. If the study is not stopped early, then the full-sample (N=400) analysis will reach an efficacy conclusion if the upper limit of the 96.07% confidence interval is smaller than 0.52 and the observed sensitivity is greater than or equal to 0.85.

If the efficacy or futility decision criteria are satisfied, then HepQuant will request the analysis data set and analysis report from the independent statistician. HepQuant will reproduce the analysis from the independent statistician and initiate the trial termination processes. If neither the efficacy nor futility criteria are satisfied, then HepQuant will remain blinded and will not receive the results of the interim analysis. The independent statistician will archive the analysis and the interim analysis data set for reference upon trial completion.

The power and type I error rate using the above interim decision criteria have been evaluated in a simulation study as described in section 9.4.2 and summarized in **Table 12**. The simulation study also calculates the probability that the trial will satisfy the interim decision criteria. **Table 13** summarizes the chance of satisfying the interim efficacy and futility decision criteria as a function of the true NLR when true sensitivity is 90%.

	Decision	s at N=250	Decisions	at N=400	Total power
NLR	Futility	Efficacy	Futilty	Efficacy	for Efficacy
		20% prevale	nce of large v	arices	
0.52	0.744	0.004	0.241	0.011	0.015
0.40	0.521	0.022	0.403	0.055	0.077
0.30	0.220	0.124	0.433	0.223	0.348
0.20	0.118	0.652	0.027	0.203	0.855
0.15	0.120	0.880	0.000	0.001	0.880
		25% prevale	25% prevalence of large varices		
0.52	0.747	0.005	0.236	0.012	0.017
0.40	0.484	0.032	0.416	0.069	0.100
0.30	0.184	0.166	0.394	0.256	0.422
0.20	0.100	0.760	0.013	0.128	0.888
0.15	0.098	0.902	0.000	0.000	0.902

Table 13: Probability of reaching the futility and efficacy decisions at the interim (N=250) and full sample(N=400) analyses. Probabilities from simulations for the indicated NLR when sensitivity = 0.90.

The interim analysis improves the efficiency of the trial by allowing early stopping for efficacy if the DSI test has NLR=0.15 (88% chance of stopping at the interim analysis with 20% large varices) or for futility under the null hypothesis of NLR=0.52 (77% chance of stopping at the interim analysis with 20% prevalence of large varices).

Statistical analyses and reporting of results: Although the confidence levels for NLR in the interim decision criteria have been adjusted to maintain the one-sided level 0.025 type I error rate, study results will be reported using 95% confidence intervals as described in section 9.4.1. Exact methods for proportions and the score-based confidence intervals for ratios of proportions will be used for 95% confidence intervals when reporting results for NLR, sensitivity, and other measures of diagnostic accuracy.

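### The binding interim futility rule is written with 'and', but Table 13's futility figures and eight Table 12 power cells reproduce only with 'or'; the 77% in the text also contradicts Table 13

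*Combined protocol and SAP*

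**What the plan says.** Section 9.5.1 allows three conclusions at N=250. Futility (criterion ii) has part (a), "The upper limit of the 51.41% score-based confidence interval for NLR is larger than 0.52, and" part (b), observed sensitivity below 0.85. The opening prose of the section describes the same conjunction: "it is futile to continue because sensitivity is too low and NLR is too large". A trial that meets neither the efficacy nor the futility criteria falls under conclusion iii: "In the case of the third conclusion, the trial will continue to the full sample of 400 subjects with complete data".

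A futility finding leaves no discretion, since "the assessment of futility represents a binding assessment", and Section 10.1.2.2 lists it among the events that stop the whole study.

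The section then says "The power and type I error rate using the above interim decision criteria have been evaluated in a simulation study". The results are in Table 12 (Section 9.4.2), captioned "Table 12: Power for the SHUNT-V trial with and without interim analyses", and in Table 13, which is restricted to one sensitivity: "Probabilities from simulations for the indicated NLR when sensitivity = 0.90". Table 13 gives interim futility at NLR 0.52 as 0.744 for 20% prevalence and 0.747 for 25%. The paragraph after Table 13 quotes a different value for futility at NLR 0.52: "77% chance of stopping at the interim analysis with 20% prevalence of large varices".

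**The concern.** With 'and', the chance of stopping for futility cannot exceed the chance that observed sensitivity falls below 0.85. At true sensitivity 0.90 that is a small tail probability, so a futility probability near three quarters looks impossible for the written rule.

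The bottom rows of Table 13 point the same way. At NLR 0.15, interim futility and efficacy add to 0.120 + 0.880 = 1.000 (20% prevalence) and 0.098 + 0.902 = 1.000 (25%), so essentially no trial continues. Under the written rule, a trial with a good NLR but observed sensitivity below 0.85 meets neither criterion and must go on to 400.

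At stake is whether the independent statistician, applying the text, takes the binding decision whose properties were presented. The stated power and the claimed efficiency of the interim analysis depend on the answer.

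**Working it through.** **Inputs.** From 9.5.1: interim at N=250, final at N=400; 97.64% interval for interim efficacy, 51.41% for futility, 96.07% for the final analysis; sensitivity threshold 0.85. From 9.4.2: score-based interval; true specificity = (1 − sensitivity)/NLR; 10,000 simulated trials; sensitivities 0.85, 0.90 and 0.95; prevalences 20% and 25%.

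**Step 1: exact bound, no simulation.** At 20% prevalence, 250 × 0.20 = 50 cases. Seven misses give sensitivity 43/50 = 0.86 and eight give 42/50 = 0.84, so condition (b) needs at least 8 misses. At true sensitivity 0.90, P(Bin(50, 0.10) ≥ 8) = 0.122. With 50 cases this is the ceiling for an 'and' rule, whatever interval is used in (a). Table 13 states 0.744 at NLR 0.52. The 0.120 in its NLR 0.15 row is close to this tail, so those stops come from the sensitivity condition alone.

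**Step 2: simulation.** Let p1 be the observed miss proportion among V cases and p2 the observed test-negative proportion among the N − V non-cases. The score statistic for NLR = 0.52 is

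T = (p1 − 0.52·p2) / √[p̃1(1−p̃1)/V + 0.52²·p̃2(1−p̃2)/(N−V)],

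with p̃1 and p̃2 the estimates restricted to p̃1 = 0.52·p̃2. An upper limit below 0.52 means T < −z, where z = 2.264 (97.64%), 0.697 (51.41%) and 2.061 (96.07%). The number of cases was drawn as Binomial(N, prevalence), with at least 200,000 trials per cell.

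The plan's own figures come first: with this set-up every without-interim cell of Table 12 and every efficacy cell of Table 13 is reproduced within 0.02.

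Interim futility, sensitivity 0.90:

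| NLR | 0.52 | 0.40 | 0.30 | 0.20 | 0.15 |
|---|---|---|---|---|---|
| 20% prevalence: Table 13 | .744 | .521 | .220 | .118 | .120 |
| 'or' | .745 | .519 | .223 | .123 | .124 |
| 'and' (written) | .123 | .123 | .118 | .012 | .000 |
| 25% prevalence: Table 13 | .747 | .484 | .184 | .100 | .098 |
| 'or' | .748 | .496 | .184 | .099 | .099 |
| 'and' (written) | .099 | .100 | .092 | .005 | .000 |

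The N=400 futility column at 20% prevalence agrees: stated .241/.403/.433/.027/.000; 'or' .240/.404/.431/.025/.000; 'and' .863/.800/.534/.072/.051. A rule using the NLR condition alone also fails, giving .011 and .000 at NLR 0.20 and 0.15.

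**Step 3: Table 12 power with the interim analysis.** All 28 cells match 'or' within 0.02; 20 match 'and'. The eight that separate the rules:

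| Prevalence | Sensitivity | NLR | Stated | 'or' | 'and' |
|---|---|---|---|---|---|
| 20% | 0.85 | 0.30 | .417 | .428 | .514 |
| 20% | 0.85 | 0.20 | .520 | .522 | .624 |
| 20% | 0.90 | 0.20 | .855 | .852 | .917 |
| 20% | 0.90 | 0.15 | .880 | .876 | .949 |
| 25% | 0.85 | 0.30 | .450 | .455 | .551 |
| 25% | 0.85 | 0.20 | .523 | .520 | .622 |
| 25% | 0.90 | 0.20 | .888 | .889 | .949 |
| 25% | 0.90 | 0.15 | .902 | .901 | .963 |

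In the other 20 cells the two rules differ by at most 0.5 point.

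**Step 4: how often the rules disagree** ('or' minus 'and' futility, 20% prevalence). At sensitivity 0.90: NLR 0.52, .745 − .123 = .622; NLR 0.20, .123 − .012 = .111; NLR 0.15, .124 − .000 = .124. At sensitivity 0.85 and NLR 0.20 it is about .48.

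**Step 5: expected sample size** at NLR 0.52, sensitivity 0.90, 20% prevalence, taking interim efficacy as .004: 'or', 250 + 150 × (1 − .745 − .004) ≈ 288; 'and', 250 + 150 × (1 − .123 − .004) ≈ 381. At sensitivity 0.85 the figures are about 287 and 328.

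**Step 6: the 77%.** At NLR 0.52 and 20% prevalence, for sensitivity 0.85/0.90/0.95, 'or' gives .749/.745/.735 and 'and' gives .477/.123/.004. The gap to Table 13 is 0.770 − 0.744 = 0.026. The simulation standard error is √(.744 × .256/10,000) = .0044, so the gap is about six standard errors.

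**The case against.** The strongest reply is that the instruction is not ambiguous. The criterion and the prose both say 'and', conclusion iii sends everything else to N=400, and Table 13 reports operating characteristics rather than giving instructions. On that view the statistician has one rule, and only the tables are wrong. The consequences are also mild: type I error is 0.020 or less in every cell under both rules, and the affected power cells are understated for the written rule, so the price of 'and' is lost efficiency within the planned maximum sample size. This stands as a limit on the harm. It does not remove the conflict, because the plan presents the tables as properties of the written rule and they are not.

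Three points of precision also stand.

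- The count of eight Table 12 cells assumes a binomial number of cases, which is the version that reproduces all without-interim cells. With a fixed number it is five to seven, in the same direction. The Table 13 conflict does not depend on this: fixing cases at 50, or using a strict inequality at 0.85, leaves futility at NLR 0.52, sensitivity 0.90 and 20% prevalence at .745 to .750 ('or') and .121 to .126 ('and').
- Agreement with 'or' is within 0.02, not always within simulation error. The .417 against .428 and the .484 against .496 are each a little over two standard errors apart. That 'or' was simulated is an inference from the fit.
- The 77% is quoted without a sensitivity, and 'or' does give 0.770 at sensitivity 0.82. The plan tabulates no such value, and the 88% in the same sentence matches Table 13 at sensitivity 0.90, so that is the natural reading.

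**Conclusion.** The concern holds. The written futility rule and the figures said to describe it cannot both be right. At sensitivity 0.90, 20% prevalence and NLR 0.52, interim futility is about 12% under the text against 74.4% in Table 13. Under the written rule, power in eight of 28 Table 12 cells would be about 6 to 10 points higher than stated. The exact bound in Step 1 needs only sensitivity 0.90 and 50 cases. The 12% ceiling is specific to sensitivity 0.90; at sensitivity 0.85 and NLR 0.52 the written rule stops about 48% of trials. The cell-by-cell figures rest on the score test and binomial case counts.

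This is not alpha inflation, and the interim efficacy probabilities, including the 88%, do not change. It still needs correcting before the interim analysis, because the decision is binding and choosing between the readings after the data are seen would make the rule data-dependent. The 77% is a separate, smaller error: it contradicts Table 13, and neither rule gives it at any tabulated sensitivity.

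**What to change.** Before the interim analysis, state one futility rule and bring Section 9.5.1 and Table 12 into line with it. The choice of rule is the sponsor's.

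- **If 'or' is intended:** change the conjunction in criterion ii and in the opening prose of 9.5.1, and replace the 77% with Table 13's figure of about 74%. The tables can stay. Cost: two words and one percentage.
- **If 'and' is intended:** keep the text, rerun the existing simulation, reissue the with-interim columns of Table 12 and all of Table 13, and replace the 77% with the new figure (about 12% at sensitivity 0.90 and 20% prevalence). The claim of efficiency under the null should be restated with it. Cost: one simulation rerun and two revised tables.

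In both cases, give the sensitivity beside the quoted percentage. Neither option changes the maximum sample size, the data collected or the efficacy criteria.
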